#### 8.3.4 RESPONSIBILITIES

Primary responsibility for AE identification, documentation, and assessment of severity and relationship to study agents can be determined by either the investigator or Medical Monitor. The medical personnel who perform these assessments must be directly involved in the clinical evaluation of the research participants.

---

#### 8.3.5 CLASSIFICATION OF AN ADVERSE EVENT

---

##### 8.3.5.1 SEVERITY OF EVENT

For adverse events (AEs), the following guidelines will be used to describe severity.

- **Mild** – Events require minimal or no treatment and do not interfere with the participant’s daily activities.
- **Moderate** – Events result in a low level of inconvenience or concern with the therapeutic measures. Moderate events may cause some interference with functioning.
- **Severe** – Events interrupt a participant’s usual daily activity and may require systemic drug therapy or other treatment. Severe events are usually potentially life-threatening or incapacitating. Of note, the term “severe” does not necessarily equate to “serious”.

---

##### 8.3.5.2 RELATIONSHIP TO STUDY INTERVENTION

The site investigator and/or Medical Monitor is responsible for assessing the relationship between the AE and the study agent(s). Site investigators must provide the initial assessment as to whether there is a reasonable possibility that the study agent(s) caused or contributed to a SAE. The relationship assessment, based on clinical judgment, often relies on the following:

- A temporal relationship between the event and administration of the study agent(s),
- A plausible biological mechanism for the agent to cause the AE,
- Another possible etiology for the AE,
- Previous reports of similar AEs associated with the study agent or other agents in the same class, and
- Recurrence of the AE after re-challenge or resolution after de-challenge, if applicable.

Further assessment of causality is provided by the DSMB based on accumulating safety reports between treatment groups.

The terms used to assess the relationship of an event to study agent are:

- Related – There is a reasonable possibility that the AE may be related to the study agent(s).
- Not Related – There is not a reasonable possibility that the AE is related to the study agent(s).

#### 8.3.5.3 EXPECTEDNESS

Expected AEs are AEs that have been previously observed with use of the study agent(s) and are listed in the package insert or Investigator's Brochure. Expectedness is not based on what might be anticipated from the pharmacological properties of the study agent or for the disease or study population under study.

An adverse event or suspected adverse reaction is considered 'unexpected' if it is not listed in the investigator brochure or is not listed at the specificity or severity that has been observed. Further details are provided in the MOP Chapter 13, Safety and Adverse Events.

**Blood draw:** Participants may experience some lightheadedness or nausea while having blood drawn. There is a risk of bruising at the site where the needle enters the skin and a remote risk of infection.

**Spirometry and maximum bronchodilation:** Participants may experience shortness of breath while doing spirometry, or, very rarely, syncope. Temporary wheezing and chest tightness occur infrequently (5% of the time). Following the bronchodilator, a transient increase in heart rate and tremor is likely (>25% chance).

**Methacholine Challenge:** Participants may experience shortness of breath, coughing, lightheadedness and dizziness. In rare cases, some participants have experienced a severe asthma attack or a reaction to the methacholine. Participants with a pre-diluent FEV1 of >50% predicted (>70% in children aged 12 to 17 years) and at least one liter will undergo the methacholine testing if they do not have a historical methacholine from testing performed under either the 2017 ERS technical standard or the 1999 ATS Guidelines.

**Sputum Induction:** Participants may experience a salty after taste in the mouth, coughing, a feeling of needing to swallow, a sore throat, shortness of breath, wheezing, chest tightness, lightheadedness, nausea or headache. In rare cases, some participants have had a severe asthma attack or a reaction to the salty water that they breathe in. Bronchodilator treatment will be available if this occurs. The following safety procedures will be followed for the sputum induction procedure:

- Adolescent participants with a post bronchodilator FEV1%  $\geq$ 70%, sputum will be induced using 3% saline; for adolescent participants with a post bronchodilator FEV1% < 70%, sputum will be induced using 0.9% saline.
- Adult participants with a post bronchodilator FEV1%  $\geq$ 50%, sputum will be induced using 3% saline; for adult participants with a post bronchodilator FEV1% < 50%, sputum will be induced using 0.9% saline.
- a physician will be available during the challenge;
- study staff will calculate and record the peak flow and FEV1 value that equals both a 10% and 20% fall in lung function based upon the recorded post-BD peak flow and FEV1 values; and
- participants will not be discharged until their FEV1 is within 10% of their post bronchodilator FEV1.

**Withholding medication:** After consenting, participants will be asked to hold certain medications prior to each visit for the purpose of lung function testing. Participants may experience an increase in their asthma symptoms from holding their daily medications. If participants are unable to hold their medications, they are instructed to take the medication as needed and to call the study staff. This will also be documented and the participant will proceed with the scheduled procedure.

Conditions common in adolescents and adults who have severe asthma will be considered expected for IND reporting purposes. Examples include sinus infections, pneumonia, and sinus surgery.

For other events, a site investigator or sub-investigator will be responsible for determining whether an adverse event (AE) is expected or unexpected. An AE will be considered unexpected if the nature, severity, or frequency of the event is not consistent with the risk information previously described for the test treatment. Test intervention-specific expected adverse events are described in the appendices.

---

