number of PFTs to be performed. Therefore, the investigators reduced the number of PFTs and visits in consideration of this feedback. The PrecISE Network also conducted one-on-one interviews with five adolescents with severe asthma and their caregivers. Overall, parents were very protective of their children and less enthusiastic about the trial. They were concerned about use of placebos but expressed that they would be willing to consider the trial if their physician recommended it. The pediatric committee considered the concerns of the caregivers and understands how important physician recommendation for the trial will be in recruitment of these patients.

The risks of study participation and the specific interventions in PrecISE are reviewed in Appendices I-V, Section 2.3, but in general, include risks of worsening asthma control, major infection, diarrhea and electrolyte abnormalities. In addition to safety lab monitoring, the overall risk of these side effects is mitigated by the short treatment periods (16 weeks) in this protocol, followed by washout periods of the study treatments.

The following sections also discuss the nonpharmacologic risks and benefits of study participation.

---

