## 7 STUDY INTERVENTION DISCONTINUATION AND PARTICIPANT DISCONTINUATION/WITHDRAWAL

### 7.1 DISCONTINUATION OF STUDY INTERVENTION

#### 7.1.1 DISCONTINUATION OF A PARTICIPANT'S ASSIGNED INTERVENTION

Participants will be monitored for safety during the trial and the occurrence of certain adverse events or laboratory abnormalities will result in discontinuation from the participant's current treatment; that is, participation in the current treatment period will stop, and the participant will enter the washout period. The following adverse events or lab abnormalities will result in discontinuation from the participant's current treatment:

1. Serious infection (including pneumonia, cellulitis, kidney or neurologic infections, and any bacteremia/sepsis).
2. Any bleeding event thought to be associated with a platelet count reduction per the judgment of the center investigator.
3. Any other adverse event, per judgment of the center investigator, requiring discontinuation from treatment.
4. Laboratory values are monitored per the schedule of activities in Section 1.3. For adults, the below lab tests will be assessed at every 4-week visit during the treatment period. Abnormalities in the following laboratory values require prompt retesting within 3 to 5 days:
  - ANC <1000/ $\mu$ L for black participants, <1500/ $\mu$ L for other participants.
  - Lymphocyte count <500/mm^3.
  - Platelet count <50,000/mm^3.
  - Hemoglobin <9.0 g/dL.
  - AST and/or ALT elevation >3 times the upper limit of normal.
  - Bilirubin  $\geq$ 2 times the upper limit of normal.
  - Calculated eGFR < 54 mL/min/1.73 m^2 and baseline eGFR was >60 mL/min/1.73 m^2 OR calculated eGFR < 50 mL/min/1.73 m^2 and baseline eGFR was 54-60 mL/min/1.73 m^2

If both tests violate the following cut-off values, the participant is removed from treatment:

- a. Two sequential platelet counts <50,000/mm^3.
- b. One platelet count <25,000/mm^3 unless the confirmatory test demonstrates a count >50,000/mm^3. Treatment must be withheld pending the confirmatory retest.
- c. Two sequential neutrophil counts <500/mm^3.
- d. Two sequential lymphocyte counts <500/mm^3.
- e. Two sequential hemoglobin assessments <8.0 g/dL or >30% below the participant's initial baseline value or the baseline value for the current treatment period.

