#### 8.3.6 SERIOUS ADVERSE EVENT REPORTING

Study investigators will immediately notify the DMCC of any serious adverse event, whether or not considered test treatment-related, including those listed in the protocol or investigator brochure. The report must include an assessment of whether there is a reasonable possibility that the test treatment caused the event.

All serious adverse events (SAEs) will be followed until satisfactory resolution or until the site investigator deems the event to be chronic or the participant is stable. Other supporting documentation of the event may be requested by the DMCC and should be provided as soon as possible.

The DMCC will be responsible for notifying the FDA of any unexpected fatal or life-threatening suspected adverse reaction as soon as possible, but in no case later than 7 calendar days after initial receipt of the information. In addition, the DMCC must notify the FDA and all participating investigators in an IND safety report of potential serious risks, from clinical trials or any other source, as soon as possible, but in no case later than 15 calendar days after the DMCC determines that the information qualifies for reporting.

---

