#### *Frequency and content of reports to the DSMB*

In advance of each meeting, the unblinded statistician at the DMCC will prepare a report for DSMB review. The report will contain the following categories of information aggregated by treatment group, where applicable:

- Current enrollment status and timeline for completion of follow-up
- Adverse events reported, both serious and non-serious, including hospitalizations and any mortality
- Major and minor protocol violations and deviations
- Numbers of participants whose study medication is discontinued

In the safety reports, the DMCC will label the treatment groups as "A", "B", etc. to lessen the chance of accidental unmasking. The unblinded DMCC statistician will provide the treatment for each code to DSMB members as needed, and the same code mapping will be used for all meetings.

Serious events are reported to the DSMB monthly, and serious adverse events that are unexpected and related to treatment are reported within 15 days from the time the DMCC is notified of the event.

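### Protocol 8.3.5.3 rules out the disease or population as a basis for expectedness, then classes common conditions of severe asthma, including pneumonia, as expected, which can switch off the expedited DSMB notice and the 7-day FDA report

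*Protocol*

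**What the plan says.** Protocol 8.3.5.3 holds two rules on what counts as an expected adverse event.

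- **Agent-information rule.** An event is expected if it has been seen with the agent and appears in the package insert or Investigator's Brochure. It is unexpected if it is not listed, or not listed at the specificity or severity observed. The section adds: "Expectedness is not based on what might be anticipated from the pharmacological properties of the study agent or for the disease or study population". Protocol 8.4.1 agrees: it defines an unexpected AE by its mismatch, in nature or severity, with the information on the agent.
- **Blanket rule.** Later in the same section: "Conditions common in adolescents and adults who have severe asthma will be considered expected for IND reporting purposes". The next sentence reads: "Examples include sinus infections, pneumonia, and sinus surgery". The investigator's own judgement of nature, severity and frequency is then assigned only to other events.

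Expectedness feeds the expedited routes. Protocol 8.3.6 gives the DMCC this duty: "notifying the FDA of any unexpected fatal or life-threatening suspected adverse reaction as soon as possible, but in no case later than 7 calendar days", counted from first receipt. Under Protocol 10.1.6, "serious adverse events that are unexpected and related to treatment are reported within 15 days from the time the DMCC is notified". Protocol 9.5.3 and SAP 7.6 also promise the DSMB prompt notice of serious events that are unexpected and related (SAP 7.6 says probably related).

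**The concern.** The blanket rule bases expectedness on the disease and population, which is the ground that the agent-information rule excludes. A safety officer cannot apply both to a pneumonia.

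Pneumonia is not a marginal example. Protocol 2.2 says that the risks of taking part and of the interventions "include risks of worsening asthma control, major infection, diarrhea and electrolyte abnormalities". Protocol 7.1.1 puts pneumonia first among the serious infections that end a participant's current treatment. The same event is therefore serious enough to stop treatment, yet classed in advance as expected for every agent.

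At stake is the speed at which an infection signal on one intervention reaches the DSMB and the FDA while that intervention is still being assigned. The class is also open-ended, because the three named conditions are given only as examples.

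**Working it through.** No arithmetic is needed for the contradiction. The check follows one case through each reporting route under each rule.

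**Case.** A serious pneumonia, judged related to the test treatment, on an agent whose brochure or insert does not list pneumonia at the observed specificity and severity.

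**Classification.** Under the agent-information rule it is unexpected. Under the blanket rule it is expected, and because the investigator's test is confined to other events, nothing later in the section reverses that.

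| Route | Condition in the text | Agent-information rule | Blanket rule |
|---|---|---|---|
| Site to DMCC, immediate (Protocol 8.3.6) | any SAE, related or not | applies | applies |
| FDA, 7 calendar days (Protocol 8.3.6) | unexpected, fatal or life-threatening, suspected reaction | applies if fatal or life-threatening | not triggered |
| FDA and investigators, 15-day IND safety report (Protocol 8.3.6) | potential serious risk that the DMCC decides qualifies; the sentence does not mention expectedness | candidate | unclear; the blanket sentence is written for IND reporting |
| DSMB, prompt notice (Protocol 9.5.3; SAP 7.6) | serious, unexpected and related (SAP: probably related) | applies (SAP: if probably related) | not triggered |
| DSMB, within 15 days (Protocol 10.1.6) | serious, unexpected and related | applies | not triggered |
| DSMB, monthly report (Protocol 10.1.6; SAP 7.6) | all serious events | applies | applies |

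**Size of the DSMB delay.** The outer limit moves from 15 days to the next monthly report, about 30 days. The difference between the two limits is 30 − 15 = 15 days. Against the prompt notice in Protocol 9.5.3, which sets no number of days, the delay could be up to about a month.

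**Size of the FDA effect.** For a fatal or life-threatening case, a report due within 7 calendar days is no longer triggered by that route. For other serious pneumonias the 7-day route never applied, so the only FDA question is the 15-day report.

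**When the rules agree.** If the agent's brochure lists pneumonia at the observed specificity and severity, it is expected under both rules and nothing is lost.

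**The case against.** Four points can be made for the plan.

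1. **Not every expedited route depends on expectedness.** A reader might infer that a related pneumonia would get no expedited report at all to the FDA or investigators. The documents do not support that. The 15-day IND safety report in Protocol 8.3.6 turns on potential serious risk and on the DMCC's decision, and its sentence does not require the event to be unexpected. The blanket sentence is aimed at IND reporting, so the loss of that report is plausible, but it is an inference. This objection stands.

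2. **A fatal pneumonia may not be a common condition.** The blanket sentence sets no severity, while the agent-information rule and Protocol 8.4.1 both make severity part of the test. That argument is fair, but it shows that the text is ambiguous, not that it is safe. Read literally, the blanket sentence has no severity limit, and the test that does consider severity is kept for other events.

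3. **Much of the safety net remains.** A reader might infer that the signal would be hidden. It would not. Sites notify the DMCC of every SAE at once. Protocol 8.3.3 has the sponsor evaluate serious events for expedited reporting. The unblinded DSMB receives SAEs monthly, and adverse event rates are compared between active and placebo periods (Protocol 9.5.3; SAP 7.6). Protocol 10.1.6 allows ad hoc meetings when SAE reporting is unusually high or unexpected, and the affected participant's current treatment stops under Protocol 7.1.1. This stands: what is lost is speed on specific routes.

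4. **The effect depends on documents not supplied.** The brochures, Appendices I–V and MOP Chapter 13 may list pneumonia for some agents or refine the rule. This also stands. The blanket sentence is written for all five interventions, but one cannot say that all five are affected.

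**Conclusion.** The point holds as an internal contradiction in Protocol 8.3.5.3 with a definite but limited consequence. The contradiction itself is certain from the text.

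The consequence is firm for two things: the expedited DSMB notice for a serious, related pneumonia, and the 7-day FDA report when that event is fatal or life-threatening. It is conditional for the 15-day IND safety report. The DSMB's outer limit goes from 15 days to about one month.

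This rests on three assumptions: staff apply the blanket sentence as written, the event is judged related, and the assigned agent's brochure or insert does not list pneumonia at the observed specificity and severity. The number of interventions that meet the last condition is unknown from the protocol and SAP. The two parts of the section must be reconciled, because they give opposite answers on a reporting duty for events that may be fatal.

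**What to change.** Amend Protocol 8.3.5.3 in one of two ways.

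- Delete the blanket sentence and its examples, so that these conditions fall under the investigator's ordinary test.
- Or relabel them as anticipated events, reviewed in aggregate by active versus placebo period in the existing DSMB reports, and state that each serious case still goes through the expectedness test.

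In either case, state that expectedness for expedited reporting is judged only against the brochure or package insert of the assigned agent, in line with the opening of 8.3.5.3 and with 8.4.1.

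The change is a one-paragraph amendment. Aggregate review needs little new work, because adverse events are already tabulated by treatment group for the DSMB and compared between active and placebo periods. The downside is a few more expedited reports, some of which will turn out to reflect the underlying disease.

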#### 8.3.5.4 TIME PERIOD AND FREQUENCY FOR EVENT ASSESSMENT AND FOLLOW-UP

The occurrence of an adverse event (AE) or serious adverse event (SAE) may come to the attention of study personnel during study visits and interviews of a study participant presenting for medical care, or upon review by a study monitor.

All AEs including local and systemic reactions not meeting the criteria for SAEs will be captured on the appropriate case report form (CRF). Information to be collected includes event description, time of onset, clinician's assessment of severity, relationship to study intervention (assessed only by those with the training and authority to make a diagnosis), and time of resolution/stabilization of the event. All AEs must be documented appropriately regardless of relationship. All AEs will be followed to adequate resolution.

Any medical condition that is present at the time that the participant is screened will be considered as baseline and not reported as an AE. However, if the study participant's condition deteriorates at any time during the study, it will be recorded as an AE.

Changes in the severity of an AE will be documented to allow an assessment of the duration of the event at each level of severity to be performed. AEs characterized as intermittent require documentation of onset and duration of each episode.

A site physician investigator or sub-investigator will record all reportable events between the time the participant provides informed consent through 8 weeks after their last treatment or a period corresponding to five half-lives of the treatment last received, whichever is longer (Section 4.1). At each study visit, the investigator will inquire about the occurrence of AE/SAEs since the last visit. Events will be followed for outcome information until resolution or stabilization.

---

#### 8.3.6 SERIOUS ADVERSE EVENT REPORTING

Study investigators will immediately notify the DMCC of any serious adverse event, whether or not considered test treatment-related, including those listed in the protocol or investigator brochure. The report must include an assessment of whether there is a reasonable possibility that the test treatment caused the event.

All serious adverse events (SAEs) will be followed until satisfactory resolution or until the site investigator deems the event to be chronic or the participant is stable. Other supporting documentation of the event may be requested by the DMCC and should be provided as soon as possible.

The DMCC will be responsible for notifying the FDA of any unexpected fatal or life-threatening suspected adverse reaction as soon as possible, but in no case later than 7 calendar days after initial receipt of the information. In addition, the DMCC must notify the FDA and all participating investigators in an IND safety report of potential serious risks, from clinical trials or any other source, as soon as possible, but in no case later than 15 calendar days after the DMCC determines that the information qualifies for reporting.

---

#### 8.3.7 REPORTING EVENTS TO PARTICIPANTS

An unexpected finding may occur whenever safety testing or imaging (CT) of the lung are done. These unexpected findings can have clear or uncertain clinical significance. For example, clear clinical significance means that the testing shows a problem that may be treatable and that we generally know what the risks are of not treating the problem. Uncertain clinical significance means that the test result is unusual or outside the boundaries of “normal”, but we do not know if it might affect the health of the participant, and treatment may not be appropriate or possible. In this study, the participant will be informed of any findings of clear clinical significance that may be discovered during the imaging procedure or safety laboratory test, but the participant will not be informed if there are findings of uncertain clinical significance. There may be benefits to learning such results (such as early detection and treatment of a medical condition), but there are risks as well (such as problems with getting insurance or employment, or becoming worried about a finding for which no treatment is required or appropriate). Participants may choose to have their physician informed of any findings of clear clinical significance that are reported. Participants will indicate their decision in the consent form regarding informing their physician and having the report placed in their medical record.

---

